The nature of the study will be explained to the participants and written informed consent will be obtained. Demographic data of each participant including age, sex, height, weight, BMI, percent body fat, lean body mass, and smoking history will be recorded. For people after stroke, the stroke type (cerebral infarction, intracerebral hemorrhage), medical history (hypertension, diabetes mellitus, cardiovascular disease, lipidemia, kidney disease) will also be recorded. The National Institutes of Health Stroke Scale (NIHSS), Modified Rivermead Mobility Index (MRMI), Modified Rankin Scale (mRS), Barthel index (BI) will be retrieved from the patient's medical record.

Participants will be invited to attend the cardiopulmonary laboratory of the hospital at a time > 2 hours after a light meal. Participants are requested to avoid caffeine-containing products, nicotine, alcohol and vigorous exercise for at least 12 hours before attending the laboratory.

Each participant will be asked to perform the lung function test to measure the FVC, FEV₁, and MIP after including the study. After completing the baseline lung function test, participant will be required to sit on the chair and rest for 15 minutes, after that, two trained researchers will use two identical ultrasonography to measure the left and right diaphragmatic thickness simultaneously at quiet breathing, the end of tidal inspiratory and the end of tidal expiratory, respectively. 3 ultrasonic images will be captured to calculate the mean diaphragmatic thickness of each breathing status. In order to determine the inter-rater reliability of the measurement of ultrasonography of

those two trained researchers, 20 participants will be chosen out randomly to receive twice diaphragmatic thickness measurement at quiet breathing, the end of tidal inspiratory and the end of tidal expiratory. However, during the second measurement, those two trained researchers will change their position to measure the contralateral side diaphragmatic thickness independently.

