After the baseline measurement, all participants will be requested to use a nose clip to hold the nose and breathe with the mouth through a pressure threshold inspiratory loading device (POWERbreathe, KH2, England). The inspiratory pressure will be set at 30%, 40%, 50%, 60%, 70%, or 80% of their MIP, in random order. Each MIP intensity protocol consists of 10 breaths. The procedure of IMT is followed by the published research protocols in people after stroke [28]. All MIP intensity protocols will be conducted in one day. A period of at least 10 minutes of rest time will be allowed between different protocols of contraction intensity (% MIP) on the same day [29].

Thickness of the left and right diaphragm (stroke and non-stroke), will be measured simultaneously by two identical ultrasonography at the end of maximum inspiration of 10 breaths of each MIP intensity protocol. The diaphragm thickness of both the left and right diaphragm at the end inspiratory breaths of the 10 breaths of each MIP intensity protocol will be recorded. Surface electromyography (sEMG) will be used to measure the activity of accessory muscle (sternocleidomastoid muscles) during each MIP intensity protocol. The % of MIP that associates with the highest calculated DTF and a relatively stable change in the activity of accessory muscles will be considered an appropriate training intensity for further IMT protocols.

The self-perceived exertion level will also be determined by the Rate of Perceived Exertion Borg scale at the end of each MIP intensity protocol [30].

All research procedures will be repeated again after 2 days to examine the test-retest reliability of ultrasonographic measurements of DTF.

Outcome measures:

[figure not shown]
Lung function

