Diaphragmatic thickness will be measured by the ultrasound machine (Mindray 9, Shenzhen, PRC). Ultrasonography is a portable, noninvasive emerging technique allowing easy and rapid estimation of muscle thickness [34, 35]. It not only can avoid the risk of exposure to radiation in medical facilities but also the reliability in providing a clear visualization of the muscle morphology at the zone of apposition [35, 36].

For consistency, all measurements will be conducted using the same transducer probe (model SuperLinear SL18-8; SuperSonic Imagine) with a bandwidth of 5 -18Hz of B mode. Ultrasonography will be performed by two trained physiotherapist who operates the machine under the guidance of a radiologist who is trained to use diagnostic ultrasound.

[figure not shown]
Participant needs to remain in the upright sitting position on the chair during the measurement procedure. To measure the right diaphragmatic thickness, the transducer probe will be placed in the right intercostal space above the eighth or ninth intercostal space, between the antero-axillary and mid-axillary lines with a 45° angle tilt between

the surface of the abdominal wall in the cephalic direction, where the diaphragm is most suitable visualized (shown in figure 1(a)). To measure the left diaphragmatic thickness, the transducer will be placed in the left intercostal space above the eighth or ninth intercostal space, between the anterior subcostal region between the anterior and midaxillary lines (shown in figure 2(a)). The diaphragm is observed as a three-layered structure, with the hypoechogenic muscular layer bordered by echogenic layers—the peritoneum and the diaphragmatic pleurae (as shown in figure 2(b) and figure 2(c)).

[figure not shown]
Figure 1 The placement of transducer probes, surface electromyography electrodes and image of the diaphragm

(a) The placement of transducer probes when measure of the right and left diaphragm by ultrasonography in people after stroke (left hemiplegia); The blue points represent the locations of surface electromyography electrodes on the sternocleidomastoid muscles.

[figure not shown]

(b) Diaphragmatic thickness images of the left diaphragm (stroke side) at the end of tidal expiration and the end of maximum inspiration at 30 %MIP.

(c) Diaphragmatic thickness images of the right diaphragm (non-stroke side) at the end of tidal expiration and the end of maximum inspiration at 30 %MIP.

Research flow chart

Reporting of adverse event:

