Though various measures will be taken to minimize the risk of adverse event throughout the study, any adverse events that might happen will be recorded.

Statistical analysis:

All data will be reported as mean \pm standard deviation (SD) unless otherwise indicated. Demographic data and clinical characteristics for all participants will be summarized using descriptive statistics. Repeated-measures ANOVA will be used to compare the differences of DTF and sEMG parameters determined at each inspiratory pressure separately. Intraclass correlation coefficient will be used to determine the inter-rater reliability of two ultrasonic operators and examine the test-retest reliability coefficient of ultrasonographic measurements of DTF recorded with different inspiratory pressures.

P value will be set at 0.05. All data will be analyzed using the IBM SPSS Statistics for Windows, Version 25.0 (Armonk, NY: IBM Corp).

References:

1. Gbd, S., Global, regional, and national burden of stroke and its risk factors, 1990-2019: a systematic analysis for the Global Burden of Disease Study 2019. *Lancet Neurol*, 2021. 20(10): p. 795-820.
2. Wu, X., et al., The hospital costs of stroke patients in Chinese island populations: an 11-year tendency analysis. *J Stroke Cerebrovasc Dis*, 2015. 24(5): p. 988-992.
3. Feigin, V., et al., Global, Regional, and Country-Specific Lifetime Risks of Stroke, 1990 and 2016. *N Engl J Med*, 2018. 379(25): p. 2429-2437.
4. Li X and Z. X., Annual data set on national mortality surveillance 2018. Beijing: China Science and Technology Press, 2019.
5. Menezes, K.K., et al., Respiratory muscle training increases respiratory muscle strength and reduces respiratory complications after stroke: a systematic review. *J PHYSIOTHER*, 2016. 62(3): p. 138-44.
6. Liu, X., et al., Assessment of Diaphragm in Hemiplegic Patients after Stroke with Ultrasound and Its Correlation of Extremity Motor and Balance Function. *Brain Sciences*, 2022. 12(7): p. 882.
7. Lista-Paz, A., et al., Pulmonary function in patients with chronic stroke compared with a control group of healthy people matched by age and sex. *Physiother Theory Pract*, 2022: p. 1-9.
8. Wilson, R., Mortality and cost of pneumonia after stroke for different risk groups. *J Stroke Cerebrovasc Dis*, 2012. 21(1): p. 61-67.
9. Saposnik, G., et al., Variables associated with 7-day, 30-day, and 1-year fatality after ischemic stroke. *Stroke*, 2008. 39(8): p. 2318-2324.

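### The planned inter-rater ICC mixes operator differences with round-to-round variation; analysing both sides of the swap together would separate out the operator bias

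*Combined protocol and SAP*

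**What the plan says.** Section 4, Procedure, of the combined protocol and SAP has the resting scans taken by two people at once: "two trained researchers will use two identical ultrasonography to measure the left and right diaphragmatic thickness simultaneously". For each breathing state, "3 ultrasonic images will be captured to calculate the mean diaphragmatic thickness of each breathing status". For inter-rater reliability, "20 participants will be chosen out randomly to receive twice diaphragmatic thickness measurement at quiet breathing" and at the tidal end-points, and at the repeat "during the second measurement, those two trained researchers will change their position to measure the contralateral side diaphragmatic thickness independently".

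Statistical analysis then says: "Intraclass correlation coefficient will be used to determine the inter-rater reliability of two ultrasonic operators". It gives no ICC form, does not say whether the ICC is calculated per side or over both sides, and includes no term for measurement round. The interval between the two rounds, and which operator starts on which side, are not given.

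Two neighbouring statements bear on the point. Procedure says "All research procedures will be repeated again after 2 days", for test-retest reliability of the thickening fraction, without fixing who scans which side on that day. The section on measuring diaphragmatic thickness says "all measurements will be conducted using the same transducer probe" and names one probe model.

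**The concern.** For any given hemidiaphragm, operator A's reading and operator B's reading come from different rounds. Their difference contains the operator effect and whatever changed between rounds: breathing pattern, posture, fatigue, or a general drift. An ICC on those pairs attributes all of it to the operators.

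The inter-rater ICC is a named analysis. It is the plan's only direct check on having different people scan the two sides, which Procedure labels stroke and non-stroke. A low value could be blamed on operators who in fact agree. If rounds drift systematically, a real operator bias could disappear on one side and look doubled on the other.

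**Working it through.** The plan states no target, expected value or precision for the ICC, so there is no figure to reproduce.

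**Inputs.** From the plan: 20 participants, two sides, two rounds, three images per reading. Assumed, because the plan gives no variances: between-person SD 0.40 mm (variance 0.16); image SD 0.10 mm, so 0.01/3 = 0.0033 for a mean of three; operator SD 0.05 mm (0.0025); round SD from 0.05 to 0.20 mm. The same operator is taken to start on the left in all 20.

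**Layout.**

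| | Left | Right |
|---|---|---|
| Round 1 | A | B |
| Round 2 | B | A |

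Let b be the operator bias (A minus B) and s the shift (round 2 minus round 1). The A minus B difference is b − s on the left and b + s on the right. Neither side alone separates b from s. The average of the two is b, if b and s are the same on both sides.

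**Random round variation.** Without it, ICC = 0.16/(0.16 + 0.0025 + 0.0033) = 0.965. With it, ICC = 0.16/(0.16 + 0.0025 + round variance + 0.0033):

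| Round SD (mm) | ICC |
|---|---|
| 0.05 | 0.950 |
| 0.10 | 0.910 |
| 0.15 | 0.850 |
| 0.20 | 0.777 |

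**Systematic shift.** Take b = s = 0.10 mm and round SD 0.05 mm, with the fixed bias replacing the random operator term. The difference d is 0.10 − 0.10 = 0.00 mm on the left and 0.10 + 0.10 = 0.20 mm on the right. For absolute agreement, ICC = 0.16/(0.16 + 0.0025 + 0.0033 + d²/2).

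- Left: 0.16/0.1658 = 0.965.
- Right: 0.16/(0.1658 + 0.02) = 0.861.
- Either side with the same bias and no shift: 0.16/(0.1658 + 0.005) = 0.937.

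Simulated means with 20 participants are 0.96 and 0.85. The left side thus looks better than the operators deserve, and the right side worse. If both sides were pooled, the average of d²/2 would be (0 + 0.02)/2 = 0.01, giving 0.16/0.1758 = 0.910. Pooling does not hide the bias, but it still charges the shift to the operators.

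**Crossed estimate.** Averaging the two sides gives (0.00 + 0.20)/2 = 0.10 mm, the true bias. Its precision at round SD 0.15 mm, over 40 hemidiaphragms, is:

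- round variation independent on the two sides: SE = √[2 × (0.0225 + 0.0025 + 0.0033)/40] = 0.038 mm;
- round variation common to both sides of a person: it cancels, and SE = √[2 × (0.0025 + 0.0033)/40] = 0.017 mm.

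With 19 degrees of freedom (t = 2.09), the 95% half-widths are about 0.08 and 0.04 mm.

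**The case against.** Much of the case on the other side stands.

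- A reader might infer that the ICC does not measure operator agreement at all. The documents do not support that. After the swap both operators have scanned every hemidiaphragm, which is an ordinary sequential inter-rater layout. Placing the probe is part of what an operator does and belongs in operator variation.
- Random round variation lowers the ICC, so it cannot falsely certify the operators. The two measurements are described as part of the resting baseline, which suggests a single sitting, and the variation may then be small. At a round SD of 0.05 mm the fall is only from 0.965 to 0.950. An approximate 95% interval around 0.95 with 20 participants is 0.88 to 0.98, which covers both.
- Exact cancellation needs a shift equal to the bias, and comparing the sides would expose it. But the plan does not commit to making that comparison, and a partial shift distorts in the same direction.
- A reader might see a contradiction between two machines and the same probe, and infer that operator and machine are confounded. The sentence goes on to name a model, so it reads naturally as one probe model on two units. At most it needs clarifying.
- No threshold or decision rests on this ICC. It covers resting scans only, and an operator bias that is constant across loads affects the within-side load comparison less.

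**Conclusion.** The concern holds in a limited form. Within a side, operator and round are confounded, and the simple ICC reports operator agreement together with round-to-round variation. Random variation makes it conservative, by 0.015 to 0.19 over the assumed range (0.965 − 0.950 to 0.965 − 0.777). A systematic shift can hide a bias on one side and inflate it on the other: 0.00 and 0.20 mm for a true 0.10 mm. The planned scans contain what is needed to recover the mean bias.

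These sizes rest on assumed variances and on one operator always starting on the same side. If starting sides varied between participants in a balanced way, a shift would no longer bias the mean difference, but it would still lower the ICC. Recovering the bias requires the operator bias and the round shift to be equal on both sides. That is open to question where one side is paretic and where the protocol describes left and right probe placement differently. This is a worthwhile and nearly free improvement to the analysis, and does not threaten the main comparison of loads.

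**What to change.** Under Statistical analysis, add for the 20 participants one mixed model per breathing state on the scans from both sides and both rounds: fixed operator, round and side; random participant, participant-by-side and participant-by-round. Report the operator bias with its 95% interval from the left/right crossing, and state the assumption that operator bias and round shift are the same on both sides. Keep the simple ICC, specify its form, and label it as between-operator, between-round reproducibility.

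Do not add an operator variance component estimated from the repeat after 2 days unless the plan fixes who scans which side on that day and the model gains a participant-by-day term.

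As clarifications only, state the interval between rounds, which operator starts on which side, and that there are two units of one probe model, with whether each stays with its side at the swap.

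The cost is slightly more analysis work and no extra scans. The interval for the bias will be of limited precision with 20 participants.

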Inspiratory muscle training (IMT) is an intervention designed for improvement of inspiratory muscle (including the diaphragm) strength and endurance in healthy adults and patients suffering from different diseases (e.g. Parkinson, chronic obstructive pulmonary disease, cardiovascular disease) [18-21]. Regarding the IMT training protocol, the commonly reported training intensities varied between 30-80% of MIP in people after stroke [22-24]. Although the diaphragm is the primary inspiratory muscle, the use of IMT may not help improve the diaphragmatic contraction under some circumstances. Previous studies suggested that, in healthy adults and people receiving mechanical ventilation, when inspiratory load exceeds the capacity of the diaphragm (higher than 60% MIP), the accessory respiratory muscle (in particular the sternocleidomastoid muscle) would be activated dramatically, which would increase work of breathing and fatigue [25, 26]. Other studies also reported that high IMT intensity may have the risk to increase the work of breathing thereby leading to fatigue [27] or resulting in a decrease, rather than increase, in surface electromyography signals in diaphragmatic activity [27]. It is postulated that IMT recruits accessory muscles such as sternocleidomastoid rather than diaphragm during the practice [24]. Hence, evaluation of effectiveness of IMT on DTF in people after stroke and further investigation on determining an optimal training protocol including inspiratory effort and training intensity for recruiting diaphragmatic activities in the stroke population are warranted.

Aims of the study:

To determine the optimal training intensity that is associated with the strongest diaphragmic thickening fraction in people after stroke.

Project significance:

Outcomes of this project study will fill the existing knowledge gaps in the understanding of the relationship between inspiratory pressure and recruitment of diaphragmatic muscles in people after sub-acute and chronic stroke.

4. Research methodology

Study design:

This study will be a cross-sectional study.

Participants:

Individuals who have had a stroke and healthy adults will be invited to participate in this study.

Participants recruitment for people after stroke:

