The inclusion criteria are: (1) age \geq 18 years; (2) clinically diagnosed with ischemic and/or hemorrhagic stroke; (3) duration of stroke range from 1 month to 12 months after diagnosis; (4) had no facial palsy, which could prevent proper labial occlusion; (5) had not undergone thoracic or abdominal surgery; (6) could understand and follow the verbal instruction; (7) stable cardiac conditions; (8) no previous history of respiratory problems.

The exclusion criteria are: (1) acute myocardial infarction or acute heart failure; (2) acute pain on chest or abdominal; (3) with the clinical signs of significant pulmonary disease; (4) consciousness impaired; (5) patient with nasal feeding tube, tracheal tube and/or any condition, which prevent the measurement or training.

Recruitment of healthy participants:

The inclusion criteria are: (1) age ≥ 18 years; (2) had not undergone thoracic or abdominal surgery; (3) no previous history of respiratory problems.

The exclusion criteria are: (1) acute myocardial infarction or acute heart failure; (2) acute pain in the chest or abdominal; (3) with the clinical signs of significant pulmonary disease; (4) unstable hypertension, arrhythmias, or unstable cardiovascular conditions, such as fluctuations in blood pressure and heart rate, indicate poor cardiac prognosis or the need for vasopressor medications; (5) pregnant.

Ethical approval:

Ethical approval will be sought from the Research Ethics Committee of Hong Kong Metropolitan University and Shenzhen Second People's Hospital.

Sample size calculation:

Sample size calculation will be based on the use of repeated-measures analysis of variance (ANOVA) using the G*Power 3.1. Considering an effect size of 0.2, an alpha error probability of 0.05 and a power of 0.80, the estimated sample size is 54 participants. An additional 20% of the sample size will be included to account for attrition. The final estimated sample size will be at least 130 participants (65 for each cohort).

Procedure:

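### Six loads in one session are ordered only at random and compared by load alone; balanced sequences and a position term would be a cheap improvement

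*Combined protocol and SAP*

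**What the plan says.** Under Research methodology, Procedure, the order is given in one sentence: "The inspiratory pressure will be set at 30%, 40%, 50%, 60%, 70%, or 80% of their MIP, in random order". Further, "Each MIP intensity protocol consists of 10 breaths" and "All MIP intensity protocols will be conducted in one day". On recovery, "A period of at least 10 minutes of rest time will be allowed between different protocols of contraction intensity". The section names no sequence list, balancing scheme or method of generating the order. The whole procedure is repeated after 2 days for reliability, and the plan does not say whether the order is redrawn.

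The Statistical analysis section reads: "Repeated-measures ANOVA will be used to compare the differences of DTF and sEMG parameters determined at each inspiratory pressure separately". It mentions no term for position in the session, sequence or preceding load.

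The result feeds a selection rule in the Procedure section: "The % of MIP that associates with the highest calculated DTF and a relatively stable change in the activity of accessory muscles" becomes the suggested training intensity. The Introduction reports earlier work, in healthy adults and ventilated people, in which loads above 60% of MIP brought in the accessory muscles, "which would increase work of breathing and fatigue".

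**The concern.** The study is labelled cross-sectional, but the comparison that answers its aim is a crossover with six periods in one session. Such a design has two familiar weaknesses.

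- **Drift.** Fatigue or learning over the session makes a reading depend on its position. With no balancing, some loads fall earlier on average than others by chance. With no position term, the drift also stays in the within-person error.
- **Carry-over.** If a block affects the next one, and heavier blocks affect it more, randomising the order does not even this out. The 80% block can affect the other five loads but never itself.

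At stake is the ranking of neighbouring loads, because the selection rule picks one load from six whose means may lie close together.

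**Working it through.** **Inputs.** Six loads, simple random order, one day and at least 10 minutes of rest come from Procedure. The load-only comparison comes from Statistical analysis. The cohort size and effect size f = 0.2 come from Sample size calculation. The documents give no drift, carry-over, DTF variance or within-person correlation, so these are assumptions shown as ranges.

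**1. The plan's own figure.** "Considering an effect size of 0.2, an alpha error probability of 0.05 and a power of 0.80, the estimated sample size is 54 participants". Then 54 × 1.2 = 64.8, rounded to 65, and 2 × 65 = 130, as stated. The 54 depends on settings that are not stated: one group with six measurements gives 55 at correlation 0 and 28 at correlation 0.5. It is not disputed here; n = 65 per cohort is used below.

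**2. Drift: expected bias.** Over all 720 orders every load has mean position 3.5. A drift of any size therefore moves all six expected means equally, and the bias between loads is exactly 0.

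**3. Drift: chance imbalance and noise.**
- Variance of one load's position: (36 − 1)/12 = 35/12. Covariance of two loads' positions in one person: −(35/12)/5 = −7/12.
- Variance of their difference: 2 × (35/12 + 7/12) = 7.
- SD of the difference in mean position: √(7/65) = 0.33 (0.36 at n = 54).
- With drift of d within-person SDs (σ) per position, the variance of a load contrast goes from 2σ²/n to (2 + 7d²)σ²/n, a ratio of 1 + 3.5d².
- At d = 0.1, 0.2 and 0.3 the ratio is 1.035, 1.14 and 1.315. The last two equal a drop from 65 people to 65/1.14 = 57 and 65/1.315 = 49.

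**4. Carry-over.** A given load immediately follows a given other load in 120 of 720 orders, a probability of 1/6, and never follows itself. If load k leaves c_k on the next block, the expected carry-over into load j is (sum of all c − c_j)/6. Let C be the size of the difference between the carry-over left by 80% and by 30%. The 80%-versus-30% contrast then shifts by C/6:
- C = 0.1, 0.3 and 0.6 total SDs gives 0.017, 0.05 and 0.10 SD.
- For comparison, at an assumed correlation of 0.5 the SE of a contrast is √(2 × 0.5/65) = 0.12 SD.
- If carry-over is linear in load, each adjacent step shifts by only C/30.
- If only the 70% and 80% blocks leave a carry-over c, the 60% load receives 2c/6 and the 70% load c/6. The whole c/6 then falls on that one step.

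**5. Does the chosen load change?** Simulations with a true peak at 60%, total SD 1, correlation 0.5 and depressing carry-over:
- *Peaked curve at the plan's f = 0.2.* The values 0, 1, 2, 3, 2, 1 have SD 0.957, so steps are 0.2/0.957 = 0.209 SD. With linear carry-over up to C = 0.6, the 60% load was picked in about 89–94% of runs, adjusted or not.
- *A harder case.* Steps of 0.117 SD, which is f = 0.117 × 0.957 = 0.112 for this shape, with carry-over from 70% and 80% only:

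| c (SD) | 60% picked, load only | 70% picked, load only | 60% picked, adjusted for position and preceding load |
|---|---|---|---|
| 0 | 71% | 14% | 68–70% |
| 0.3 | 62% | 24% | 68–70% |
| 0.6 | 49% | 37% | 68–70% |

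**6. What each remedy does.** A Williams square equalises position, but it leaves the expected C/6 shift in place. With linear carry-over at C = 0.6, the load-only 80%-minus-30% estimate was about 0.31 SD against a truth of 0.209. With position and preceding load in the model it was 0.20–0.21, and the SE stayed at about 0.12–0.13 SD.

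**The case against.** The strongest reply is that the design already protects the comparison. Order is random, each block is short, and the rest has a cited basis. The plan nowhere says that fatigue outlasts that rest. The Introduction's remark on fatigue reports other populations and says nothing about recovery. The title of the reference cited for the rest period suggests that diaphragm recruitment rises during a bout, so any carry-over could be facilitating. The selection rule also requires stable accessory activity, which may work against the top loads. Even with C as large as 0.6 SD, the end-to-end shift is below one SE.

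Most of this stands. A reader might infer that the plan biases the load–DTF curve toward the highest loads. The documents do not support that: drift gives no expected bias, and a tilt toward high loads needs depressing carry-over that persists past the rest. With facilitating carry-over the tilt reverses. Nor do the documents say that the orders are unbalanced; they are silent on balancing.

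The reply does not show that the plan would detect or allow for these effects. An unknown sign is a reason to estimate carry-over, and under a threshold pattern the shift is not spread thinly.

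**Conclusion.** The point holds as a cheap improvement, not as a demonstrated bias. The order scheme and the handling of position and carry-over are unspecified.

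- **Drift** costs precision and leaves chance imbalance (SD 0.33 positions). The variance ratio is 1.14 to 1.315 if d is 0.2 to 0.3, and 1 if there is no drift.
- **Carry-over** shifts 80% versus 30% by one sixth of the carry-over difference, at any sample size. Its size and sign are unknown.

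The effect on the chosen load runs from negligible, with steps of 0.209 SD and linear carry-over, to material, with small steps and carry-over from 70% and 80% only. These results rest on first-order carry-over, an assumed correlation of 0.5 and assumed values of d, C and c.

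**What to change.** 1. **Order.** Replace the random-order wording with allocation to the six sequences of a Williams square, in permuted blocks of six within each cohort. Each load then occurs equally often in each position and directly follows every other load equally often. Exact balance needs a multiple of six: 66 per cohort, 132 in all, which the stated minimum of 130 allows. With 65, or after attrition, balance is near but not exact.
2. **Records.** Keep the sequence, the position and the actual rest time for each block.
3. **Main analysis.** Fit DTF and sEMG with a linear mixed model that has load and position as factors and participant as a random effect. Use the position-adjusted load estimates when applying the selection rule, with both of its conditions.
4. **Sensitivity analysis.** Prespecify the same model with the immediately preceding load added, and report whether the selected load changes. Balance and the position term do not remove carry-over, so this step is needed. It is kept secondary because adjusting for carry-over is debatable.

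**Cost.** A new sequence list, one more person per cohort if exact balance is wanted, a mixed model in place of the standard repeated-measures ANOVA, and a few degrees of freedom. Intervals may widen slightly when the preceding-load term is fitted. No extra visits or procedures are needed.
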